5.2 Schedule

The Investigator is responsible for completing the cohort summary template and submitting to the IND office Medical Monitor for review and approval prior to advancing subjects to the next protocol specified cohort/dose level. A copy of the cohort summary should be placed in the Investigator's Regulatory Binder under "sponsor correspondence". This should be submitted after the first six patients.

5.2.1 Patients will be treated according to the following schedule:

- 5-azacytidine will be administered subcutaneously (SQ) or intravenously (IV) for 7 days of every cycle with daily schedule of 7 consecutive days (Days 1-7) or for days 5-2-2 which is 5 consecutive weekdays (Days 1-5) with rest on the 2 weekend days (Days 6 and 7) and then dosing the first two weekdays of the next week (Days 8 and 9) of each 28-day cycle as determined by treating physician. Alternative dosing schedules such as 4-2-3 which is 4 consecutive weekdays (Days 1-4) with rest on the 2 weekend days (Days 5 and 6) and then dosing the first three weekdays of the next week (Days 7, 8, and 9) of each 28-day cycle or other schedules allowing the 2 day weekend interruption may be applied as long as we make every attempt to give the 7 days of azacytidine as consecutively as possible. This must be clearly documented in the medical record as determined by treating physician after approval from the PI. Both SQ

and IV forms of administration are FDA approved and considered interchangeable. Patients may start receiving 5-azacytidine by one route and changed to the other, and also administration schedules from one schedule and changed to the other at any time as needed based on patient and/or physician preference.

- Avelumab will be administered as an approximately 60 minute (+/- 30 minutes) IV infusion on Day 1 and day 14 (+/-3 days) of each 5-azacytidine cycle for the first 4 cycles or until CR (whichever occurs earlier) followed by a maintenance regimen (one dose of avelumab on day 1 of each cycle of 5-azacytidine). Patients who have evidence of budding relapse or seem to have clinical benefit may continue or revert back to receiving avelumab on Day 1 and day 14 (+/-3 days) of each cycle of 5-azacytidine. Patients may receive avelumab more or less frequently during the maintenance regimen only after discussion with the PI. Avelumab will be administered every cycle with no interruptions unless there are adverse events as described in Section 5.3.

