Investigators should, whenever possible, determine which medication is causing the toxicity and interrupt or dose reduce 5-azacytidine and/or interrupt avelumab, as applicable. No dose reductions (only interruptions) are permitted for avelumab in the phase II portion after RP2D has been established.

Dose reductions of azacytidine [to be implemented in the phase II portion of the study](#) will be as follows: dose level -1 of azacytidine: 50 mg/m², dose level -2: 37.5 mg/m², dose level -3: 25 mg/m².

Table 2 Dose adjustments of azacytidine for non-hematologic drug-related AEs, clinically significant in the opinion of the investigator

Grade	Occurrence	Dose modification
1 or 2	Any time	No dose reduction
3 or 4 (Persistent grade 2: Consider similar dose adjustments if persistent and not responding to optimal management in the opinion of PI and treating physician)	1st and 2nd time	Hold 5-azacytidine. Resume 5-azacytidine at prior dose if recovery to \leq Grade 1 occurs within 14 days. If toxicity persists for 15-28 days, hold therapy and resume 5-azacytidine at prior dose if recovery to \leq Grade 1 OR resume 5-azacytidine at ONE dose level below current dose if recovery to \leq Grade 2. Dose re-escalation to prior dose of 5-azacytidine is permitted in accordance with the dose-escalation guidelines in section 5.3.6.
	3 rd and 4th time	Hold 5-azacytidine. Follow until toxicity \leq Grade 2. Resume 5-azacytidine at ONE dose level below current dose. Dose re-escalation of 5-azacytidine to prior dose is permitted in accordance with the dose-escalation guidelines in section 5.3.6..
	5th time	Discontinue therapy

5.3.3 Avelumab dose delay/interruption for immune-oncology drug-related AEs, clinically significant in the opinion of the investigator

Avelumab administration should be delayed for the following drug-related AEs, clinically significant in the opinion of the investigator:

- Any Grade \geq 2 non-skin AE, except that
 - Grade 2 fatigue or laboratory abnormalities do not require delay, however
 - Patients with ALT or AST > 3 and up to 5 x ULN or total bilirubin greater > 2.0 mg/dL and up to 3 x ULN or creatinine > 2.0 mg/dL and up to 3 x ULN should have avelumab treatment withheld.

Avelumab administration should be delayed for the following drug-related AEs, clinically significant in the opinion of the investigator:

- Any Grade 3 skin AE, or Grade 3 laboratory abnormality, with the following exceptions:

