5.3.4 Avelumab Discontinuation Criteria

The following ADRs require permanent treatment discontinuation of avelumab:

---**Any Grade 4 AEs require treatment discontinuation with avelumab** except for single laboratory values out of normal range that are unlikely related to study treatment as assessed by the Investigator, do not have any clinical correlate, and resolve within 7 days with adequate medical management

---**Any Grade 3 AEs require treatment discontinuation with avelumab except for any of the following:**

- Transient (≤ 6 hours) Grade 3 flu-like symptoms or fever, which is controlled with medical management
- Transient (≤ 24 hours) Grade 3 fatigue, local reactions, headache, nausea, emesis that resolves to Grade ≤ 1
- Single laboratory values out of normal range (excluding Grade ≥ 3 liver function test increase) that are unlikely related to study treatment according to the Investigator, do not have any clinical correlate, and resolve to Grade ≤ 1 within 7 days with adequate medical management
- Tumor flare phenomenon defined as local pain, irritation, or rash localized at sites of known or suspected tumor
- Change in ECOG PS to ≥ 3 that does not resolve to ≤ 2 within 14 days (infusions should not be given on the following cycle, if the ECOG PS is ≥ 3 on the day of study drug administration)

Any Grade 2 AEs should be managed as follows:

- If a Grade 2 AE resolves to Grade \leq 1 by the last day of the current cycle, treatment may continue.
- If a Grade 2 AE does not resolve to Grade \leq 1 by the last day of the current cycle, infusions should not be given on the following cycle. If at the end of the following cycle the event has not resolved to Grade 1, the subject should permanently discontinue treatment with avelumab AE (except for hormone insufficiencies, that can be managed by replacement therapy; for these hormone insufficiencies, up to 2 subsequent doses may be omitted).
- Upon the second occurrence of the same Grade 2 AE (except for hormone insufficiencies that can be managed by replacement therapy) in the same subject, treatment with avelumab has to be permanently discontinued.
- Infusion-related reactions, hypersensitivity reactions (Grades 1 to 4), and tumor lysis syndrome should be handled according to guidelines provided.
- Any dosing interruption lasting $>$ 8 weeks with the following exceptions:

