7.1.6 Pretreatment optional correlative studies (see below)

7.1.7 Electrocardiogram (EKG)

7.1.8 Routine urinalysis

7.1.9 Chest X-ray

7.1.10 TSH, free T3, free T4, free & total cortisol

7.1.11 Respiratory PCR panel

7.2 Evaluation During Treatment

7.2.1 Physical exam at the start of each cycle (± 4 days) and documentation of all concomitant medications.

7.2.2 CBC, platelet count, differential twice weekly (± 4 days) for the first 3 cycles, then every 2-4 weeks (differential can be omitted if WBC is $\leq 0.5 \times 10^9/L$)

7.2.3 Creatinine, total bilirubin, ALT, or AST, calcium, magnesium, glucose, BUN, uric acid, fractionated bilirubin, alkaline phosphatase, sodium, potassium, chloride, bicarbonate twice weekly (± 4 days) for the first 3 cycles, then every 2-4 weeks.

7.2.4 TSH, free T3, free T4, and free & total cortisol once monthly (± 4 days) for the first 3 cycles, then every 3 months (± 4 days).

7.2.5 Bone marrow aspiration on day 28 (± 7 days), then every 1-4 cycles. Bone marrow tests can be ordered more frequently if mandated by development of peripheral blood counts. No repeat bone marrow is necessary if nonresponse or progressive disease can be unequivocally diagnosed from peripheral blood tests or, in patients with a WBC < 0.3 if the bone marrow test is considered noncontributory by the investigator at any time point.

7.2.6 Concomitant medication data will not be collected or entered into the case report form except for concomitant hydroxyurea; however, the subject's medication record will contain a list of concomitant medications.

Correlative Studies relating to immunologic response (Optional):

Tumor tissue, blood samples and bone marrow aspirate will be collected from patients under Z20160444 and will be sent to [name] lab at MD Anderson for research

purposes (described below). Patients will be consented separately on this IRB approved consent for collection of additional material. Correlative laboratory studies will be conducted under this clinical trial protocol as described below.

7.2.7 Patients may participate in the clinical study protocol irrespective of whether they choose to participate in the correlative studies. In tumor tissues, immunohistochemical studies will be performed to evaluate tumor and immunological cell markers such as CD4 and CD8 T cells. In peripheral blood, we will also evaluate tumor and immune cell populations including but not limited to CD4 and CD8 T cells in pre and post therapy samples.

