is unable to return to MDACC the follow-up visits may be conducted via telephone. Every 3-6 months for up to 5 years after last dose of study drug patient will have a physical exam and blood (about 1-2 teaspoons) will be drawn for routine testing. If the patient is unable to return to MD Anderson, they may be called by a member of the research staff and asked how they are feeling.

Table 6. The study assessment schema is shown in tabular form below

Study Period/Cycle	Screening*	Treatment																	End of Study (EOS) ^{h,i}	Long-Term Follow-Up	
		Cycle 1						Cycle 2						Cycle 3							Subsequent Cycles ^k
Cycle Day		1	8	14	15	22	28	1	8	14	15	22	28	1	8	14	15	22	1	30 Days After Last Dose	Every 3-6 months
Study Day	-14 to 0	1	8		15	22		29	36		43	50		57	64	70	71	78	—		
Complete history	X	X						X						X					X		
Physical examination ^a	X	X						X						X					X	X	
Vital Signs ^{**}		X		X				X		X				X		X			X		
Performance status	X	X						X						X					X	X	
Document all measurable disease (if present)	X																				
Concomitant medications ^a	X	X						X						X					X		X
ECG ^l	X							X						X					X		
CBC with differential ^b	X	X	X		X	X		X	X		X	X		X	X		X	X	X	X	
Sodium, Potassium, Chloride, glucose, uric acid, bicarbonate, BUN, Creatinine, total bilirubin, direct bilirubin, calcium, magnesium, ALT ₇ or AST, alk phos ^b	X	X	X		X	X		X	X		X	X		X	X		X	X	X	X	
Routine Urinalysis	X	X						X						X					X		
TSH, free T3, free T4 ^c , free & total cortisol		X						X						X					X		
Pregnancy test ^d	X																				
Bone marrow aspirate/biopsy ^e	X						X												X		

Correlative	Screening	Cycle 1				Cycle 2				Cycle 3				Subsequent cycles	EOS
Optional correlatives on blood ^f	X			Day 14	Day 21-28			Day 14		No		No		Day 1 and 14 of cycles 4, 8, 12	If possible
Chest X-ray	X														
Respiratory PCR panel	X														
Optional correlatives on bone marrow ^g	X				C#1 Day 28			C#2 Day 28				C#3Day 28	Day 28 of cycle 6, 12	If possible	

* Samples collected at screening do not need to be repeated on Day 1 of Cycle 1.

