** During the first infusion patient vital signs should be monitored prior to dosing, approximately 15 minutes after initiation of the infusion (then approximately every 15-20 minutes as indicated), at approximately 60 and 120 minutes after completion of the infusion, or longer if indicated, until the vital signs normalize or return to baseline. For subsequent infusions, vital signs should be collected prior to dosing, approximately every 30 minutes during dosing, and approximately 1 hour post dosing.

^a A complete physical examination and documentation of concomitant medications will be done on day 1 of each cycle (+/- 4 days).

^b The specified labs must be done at least twice weekly (+/- 4 days) for the first 3 cycles, then every 2-4 weeks on subsequent cycles. The labs may be done more frequently than twice a week at the discretion of the treating physician and/or the PI.

^c TSH, free T3, free T4 will be done at least once monthly (+/- 4 days) after the start of therapy for the first 3 cycles, then every 3 months (+/- 4 days) on subsequent cycles.

^d Pregnancy test either urine or plasma should be done in women of childbearing potential 72 hours before initiation of protocol therapy.

^e Bone marrow aspiration must be done within 28-days (+/- 7 days) of initiation of therapy, then Day 28 (+/- 7 days) every 1-4 cycles. Cytogenetics may be used from prior bone marrow analysis if these were not reported on the screening bone marrow.

^f Correlative studies will be collected on peripheral blood at baseline (prior to 5-azacytidine dose), on day 14 (prior to avelumab), and between days 21 to 28 on cycle 1. Subsequently, peripheral blood will be obtained on days 1 and 14 of cycles 2, 4, 8, 12, and at progression if possible. All these tests can be +/- 5 days. Additional samples may be collected if the disease gets worse.

^g Correlative studies will be collected on bone marrow at baseline, day 28 (+/- 5 days), then on day 28 (+/- 5 days) of cycles 3, 7, 11 and at progression if possible.

^h EOS visits include a physical examination, CBC with differential and platelets and a limited chemistry profile (total bilirubin, serum creatinine, SGPT or SGOT). A bone marrow aspiration may be done if non-response or progressive disease cannot be unequivocally diagnosed from peripheral blood.

ⁱ Subject will be followed for toxicity for at least 30 days after the last protocol treatment. The 30-day follow-up visit (+ or - 3 days) will be scheduled as a

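### Table 6 shows weekly labs where the text requires twice weekly, and no draw is tied to the Day 14 avelumab dose; from cycle 4 that dose may rest on a Day 1 result about 13 days old

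*Combined protocol and SAP*

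**What the plan says.** All references are to the Combined protocol and SAP.

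- **Frequency in the text.** Section 7.2.2 asks for "CBC, platelet count, differential twice weekly (± 4 days) for the first 3 cycles, then every 2-4 weeks". Section 7.2.3 ends its chemistry list with "bicarbonate twice weekly (± 4 days) for the first 3 cycles, then every 2-4 weeks". Footnote b of Table 6 applies the same frequency to both laboratory rows as a minimum: "The specified labs must be done at least twice weekly (+/- 4 days) for the first 3 cycles, then every 2-4 weeks". Its next sentence lets the treating physician or PI order more.
- **Marks in Table 6.** The "CBC with differential" row and the chemistry row are marked at screening, on Days 1, 8, 15 and 22 of cycles 1-3, on Day 1 of subsequent cycles, and at end of study. Their Day 14 cells are blank. In the main grid the Day 14 columns carry vital signs only.
- **Dosing.** Section 5.2.1 gives avelumab "on Day 1 and day 14 (+/-3 days) of each 5-azacytidine cycle for the first 4 cycles", or until CR if that is earlier, and then on Day 1 only. Patients with signs of relapse or with benefit may keep or return to two doses per cycle.
- **Hold rules.** Under section 5.3.3, patients with ALT/AST, bilirubin or creatinine in stated ranges "should have avelumab treatment withheld"; higher values call for interruption.
- **Research sample.** Section 7.2.7 and footnote f place an optional research blood sample on Day 14, ahead of the avelumab dose.
- **Flexibility.** Section 7.0 does not count laboratory tests done off schedule as deviations. Section 7.2.9 lets laboratory work move to a local clinic after cycle 1. Section 7.2.8 and footnote k let testing fall to one set per cycle after six months without significant toxicity.

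**The concern.** The 5.3.3 rules work only if a reasonably current chemistry result is available when the second dose of a cycle is due. The schedule does not supply one by design: the mark closest to the Day 14 infusion falls a day after it. The protocol fixes pre-dose timing on Day 14 for an optional biomarker sample, but not for the tests on which its own hold rule depends.

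Two further features make this worse. Staff working from the table would draw half as often as the text requires. The dense testing also stops after cycle 3, one cycle before the planned two-dose period ends, and no exception is made for patients who stay on or return to two doses. What is at stake is whether a liver or renal abnormality is known before re-exposure, and whether the sponsor can show that the hold rules were applied as written.

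**Working it through.** The plan states no figure for this interval, so there is none to reproduce. The check sets the schedule passages side by side and counts days.

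**Inputs**

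| Item | Value | Source |
|---|---|---|
| Table draws, cycles 1-3 | Days 1, 8, 15, 22 | Table 6 |
| Table draws, later cycles | Day 1 | Table 6 |
| Required frequency, cycles 1-3 | at least twice weekly, ±4 days | 7.2.2, 7.2.3, footnote b |
| Required frequency, later | every 2-4 weeks | same |
| Second avelumab dose | Day 14 ±3, i.e. Days 11-17 | 5.2.1 |

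**Step 1: frequency.** Twice weekly means a spacing of 7/2 = 3.5 days, or 28/3.5 = 8 draws per 28-day cycle. Table 6 shows 4. The two differ by a factor of 2.

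**Step 2: window against spacing.** The window is ±4 days and the spacing 3.5 days. Because 4 > 3.5, a draw may move past the nominal date of its neighbour, so the frequency does not fix where a draw falls relative to the dose.

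**Step 3: cycles 1-3.**
- Table marks alone: the last mark before the dose is Day 8, and 14 - 8 = 6 days.
- Text: assuming even spacing (Days 1, 4.5, 8, 11.5, 15), the last draw before the dose is Day 11.5, and 14 - 11.5 = 2.5 days.
- Window, assuming it applies to each draw separately: the Day 11.5 draw may be as late as 11.5 + 4 = Day 15.5, after a Day 14 dose. The Day 8 draw may be as early as 8 - 4 = Day 4. The gap can then reach 14 - 4 = 10 days. This is a stacked extreme and shows only that recency is not guaranteed.
- The Day 15 mark with its window covers Days 11-19 and overlaps the dose window of Days 11-17, so that draw may fall on either side of the infusion.

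**Step 4: cycle 4 and later two-dose cycles.**
- Day 1 draw to Day 14 dose: 14 - 1 = 13 days.
- Across the dose window: 11 - 1 = 10 to 17 - 1 = 16 days.
- Next required draw, 2 to 4 weeks after Day 1: Day 1 + 14 = 15 to Day 1 + 28 = 29. Even the shortest interval lands after the nominal Day 14 dose.

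**Step 5: doses by testing regime.** Without an earlier CR there are 4 planned Day 14 doses. Three (cycles 1-3) fall under twice-weekly testing. One (cycle 4), plus any continued or resumed Day 14 dose, falls under testing every 2-4 weeks.

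**The case against.** The best defence is that footnote b and sections 7.2.2/7.2.3 govern, not the grid. Read that way, a result about 2.5 days old is nominally available in cycles 1-3, and physicians may order more. Known abnormalities also bring closer checks under Table 3: every 3 days for Grade 2 liver tests and every 1-2 days for Grade 3-4. Avelumab administration details are further referred to a dosing manual (Appendix H) that is not part of the text available here, and it may contain a pre-dose check.

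Much of this stands, and it rules out several stronger readings that a reader might infer:

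- **That no scheduled result precedes the Day 14 dose.** Day 8 and the twice-weekly minimum supply results in cycles 1-3, and Day 1 supplies one in cycle 4. The issue is age, not absence.
- **That the gap in cycles 1-3 is 13 days.** (14 + 3) - (8 - 4) = 13 uses table marks alone, ignores the twice-weekly draws, and needs the Day 15 draw to fall after Day 17.
- **That all four Day 14 doses are equally exposed.** Three fall under the denser schedule, and an earlier CR reduces the number.
- **That DLT assessment is compromised because the causal dose is unclear.** Sections 5.2.1.3-5.2.1.4 count DLTs per patient on the combination, and no rule assigns a DLT to a particular avelumab dose.
- **That performance status has the same gap.** The 5.3.4 clause refers to status "on the day of study drug administration" but concerns infusions in the following cycle, and Table 6 marks performance status on Day 1 of each cycle.

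The defence does not remove the conflict between table and text, the window that exceeds the spacing, or the drop in testing before two-dose treatment ends. The Table 3 checks start only once an abnormality has been found.

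**Conclusion.** The point holds in a limited form. Table 6 contradicts the written minimum by a factor of two (4 against about 8 draws per 28 days). No count or chemistry draw is linked to the Day 14 infusion in the available text. In cycles 1-3 this leaves recency unassured. From cycle 4 it is a clear gap: the latest required result can be 13 days old at nominal timing, with a range of 10 to 16 days.

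These figures assume that the Day 1 draw is taken on Day 1, that no extra tests are ordered, and that Appendix H adds no requirement. No planned analysis or MTD decision is shown to change. It is a schedule inconsistency with a safety consequence, and it should be corrected.

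**What to change.** Reconcile Table 6, footnotes b and k, and sections 7.2.2 and 7.2.3 with sections 5.2.1 and 5.3.3. Leave every hold limit as printed.

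1. Use one draw frequency in both table and text, with a window narrower than the interval between draws.
2. Align the Day 15 count and chemistry mark with the Day 14 dosing visit.
3. State which scheduled result serves each Day 14 dose, including cycle 4 and any later two-dose cycle, and make footnote k consistent with that statement.

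The sponsor sets the clinical timing. The request is that the passages agree, not that a new dosing rule be added.

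Cost: table and footnote wording. Moving the Day 15 mark adds no draw in cycles 1-3. Cycle 4 and later two-dose cycles need at most one extra blood draw each, at a visit that already takes place.
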